9.1.8. Low Back Pain VAS

Low back pain VAS will be collected at each visit.

Collection Method: Subject completes a form without assistance, and the results are transferred to the eCRF.

9.1.9. Medication

All prescribed medications used, regardless of indication, will be collected at the time of Subject Screening/Baseline Visit.

Medication endpoints will use the subset of this data comprised of prescribed pain medications and muscle relaxant

- Primary endpoint assessment - the metric will be based on all prescribed pain medications or muscle relaxants taken.
- Secondary endpoint assessment - the metric will be limited to opioids taken for treatment of low back pain.

Collection Method: Question asked by the Study Coordinator and recorded then transferred to the eCRF.

9.1.10. Treatment Satisfaction Questionnaire

Treatment Satisfaction Questionnaire will consist of the questions shown in Figure 6.

Are you satisfied with the outcome of your treatment?		
 Definitely yes	 Maybe	 Definitely not
Knowing what you know now, would you want this treatment again?		
 Definitely yes	 Maybe	 Definitely not
Would you recommend this treatment to another person with chronic low back pain?		
 Definitely yes	 Maybe	 Definitely not

Figure 6: Treatment Satisfaction Questionnaire

Collection Method: Subject completes a paper form and results are transferred to paper CRF or into the eCRF

9.1.11. Subject Global Impression of Change

Subject Global Impression of Change consists of the questionnaire as detailed in 4.6.5.

Collection method: Subject completes a paper form and results are transferred to paper CRF or eCRF

9.1.12. Clinical Global Impression – Global Improvement

Clinical Global Impression – Global Improvement consists of the questions that are to be completed by the Investigator as shown in Figure 3 on Page 28.

Collection method: Physician completes on a paper CRF which is transferred to eCRF

9.1.13. EQ-5D

The EQ-5D-5Lⁱ Quality of Life questionnaire is completed by the Subject. Validated language specific versions are available.

Collection method: Subject completes a paper form and results are transferred into the eCRF

9.1.14. Adverse Events

All transient and long-term adverse events will be collected throughout the course of the study. Assessment will include Investigator-assessed relationship to device, relationship to procedure, severity (i.e.: AE or SAE), subsequent treatment/intervention required and resolution status at each follow-up visit until the event is resolved or closed because of chronic nature of the event. Note that a Subject death automatically closes any outstanding adverse events for that Subject.

Collection Method: Paper CRF or eCRF

9.1.15. Device Deficiency

Device deficiency data collection will include all device deficiencies, including suspected device malfunctions and deficiencies.

Collection Method: Paper CRF or eCRF

9.2. Management of Protocol Deviations

An Investigator is required to conduct this study in accordance with the signed Investigator's Agreement, this investigational plan, applicable laws and applicable national regulations, and any conditions of approval imposed by the reviewing IRB or Ethics Committee and regulatory agency (e.g.: FDA or Competent Authority).

Protocol deviations are a fact of life with any clinical trial. Deviations may be anticipated (e.g.: known delay in a follow up visit), inadvertent (e.g.: unplanned delay or miss of a follow up visit due to a family emergency), or unanticipated on an emergency basis (e.g.: trauma may require device removal to allow an MRI, or other contraindicated procedures).

Except in emergency situations, protocol deviations require prior Sponsor approval; and if the deviation may affect the scientific soundness of the plan or the rights, safety, or welfare of Subjects, prior IRB or Ethics Committee approval is required.

An Investigator shall notify the Sponsor and the reviewing IRB or Ethics Committee of any deviation from the investigational plan to protect the life or physical well-being of a Subject in an emergency. Such notice shall be given as soon as possible, but no later than five working days after the emergency occurred.

All deviations from the investigational plan must be reported to the Sponsor together with the reason for the deviation and possible corrective actions for the deviations. In some circumstances, the center may be required to notify the center's IRB or Ethics Committee, and the Sponsor will notify the appropriate regulatory agencies.

i See <http://www.euroqol.org/>

9.3. Informed Consent

Informed Consent is required from all Subjects (or their legal representatives) prior to the Subject's participation in the study. The process of obtaining Informed Consent shall comply with the Declaration of Helsinki, FDA 21CFR 50, ISO 14155-2011 and applicable national regulations (local IRB, Ethics Committee and/or Regulatory bodies, as applicable).

The process of obtaining informed consent shall

- a) Avoid any coercion of or undue influence of Subjects to participate,
- b) Not waive or appear to waive Subject's legal rights,
- c) Use native language that is non-technical and understandable to the Subject or his/her legal representative,
- d) Provide adequate time for the Subject to consider participation and ask questions if necessary,
- e) Informed consent shall always be signed and personally dated by the Subject or legal representative and by the Investigator or delegate.

The original signed Informed Consent must be retained on file by the Investigator and a copy given to the Subject (Investigator's responsibility).

9.4. Subject Classification

All Subjects are classified as one of the following:

- Baseline withdrawal – refers to a Subject who has been enrolled but then is withdrawn from the study before the device implant process has been initiated. The original Informed Consent form for intent Subjects should be maintained in the Centre's administrative files. There are no follow-up requirements for Baseline withdrawal Subjects.
- Attempt – refers to a Subject who has been enrolled, and in whom a ReActiv8 implant was attempted (i.e.: attempt to place at least one lead) but was not completed.^j All Subjects in whom the implant was unsuccessful will be followed for at 30 days following the implant attempt. If there are any AEs or SAEs associated with the attempted implant, the Subject will be followed until resolution or closure of the AE or SAE.
- Implant – refers to an enrolled Subject whose implant was completed (i.e.: device remains implanted and the surgical wound is closed and dressed).
- Withdrawal post implant – refers to a Subject who is determined to be inactive in the study due to physician discretion, Subject choice, lost to follow-up, or Subject death. Final status information will be included on all Subjects as available per the Informed Consent document.

9.5. Subject Data Confidentiality

Throughout the study, confidentiality shall be maintained at all times, by all parties involved, and all data shall be secured against unauthorized access. Confidentiality of each Subject shall be preserved in reports and any publication of the results. Only authorized personnel and their designees will have access to these confidential files. Subject data may be made available to national and foreign regulatory agencies, health or other governmental authorities, under strict confidentiality condition. The investigational sites shall ensure that data (e.g. worksheets,

^j Only one procedure for ReActiv8 implant should be attempted for each Subject, although each procedure may include multiple attempts to implant, e.g.: to allow for surgical challenges and need for lead repositioning.

programmer printouts, medical records, digital images) forwarded to the Sponsor do not contain any Subject identifying data (such as name and birth date) other than the Subject ID.

It is required that CRFs be entered in the electronic data entry system provided by the Sponsor. All CRFs require the Investigator's signature or the Investigator's designee.

Source documents as per FDA 21CFR 812 and ISO 14155-2011 are printed, optical or electronic documents including the information in original records and necessary for the reconstruction and evaluation of the clinical investigation. Original source data should remain at the investigational site.

Any changes of the reported data should be reported to the Sponsor. When available, changes should be entered into the electronic discrepancy management system provided by the Sponsor. A participating Investigator shall provide direct access to source data and documents for Trial-related monitoring, audits, IRB or Ethics Committee review, and regulatory inspection.

All Subjects' health information will be kept confidential in accordance with all applicable laws and regulations. Subjects' health information may be used to conduct this research, as well as for additional purposes, such as overseeing and improving the performance of products, new medical research and proposals for developing new medical products or procedures, and other business purposes. Information received during the study will not be used to market to Subjects; Subject names will not be placed on any mailing lists or sold to anyone for marketing purposes.

9.6. Record Keeping

Investigators are required to maintain on file the accurate, complete, and current records relating to this investigation:

- All correspondence with another Investigator, an IRB or Ethics Committee, Mainstay Medical, a monitor, or FDA or Competent Authority including required reports
- The signed CIP with any and all amendments
- The approved template of the Subject informed consent form
- Records showing receipt, use, and disposition of all devices (including software), including:
 - Date, quantity, and serial numbers of devices received
 - Names of all persons who received, used or disposed of each device
 - Dates and serial numbers of devices returned to the Sponsor and the reason(s) for return
- IRB or Ethics Committee approval of the CIP and any amendments and renewals
- Competent Authority Approval in those countries where is applicable
- The Investigators' agreement and the fee agreement (separate or combined)
- The Report of Prior Investigations and/or the Investigator's Brochure
- The insurance certificate
- The Implant and Programming Manual and any other documentation provided with the device
- Current curriculum vitae for the principal Investigator and all Sub-investigators
- Monitoring letters (if applicable)
- Interim/final reports
- Study initiation forms
- Study closure documents

In addition, to the study administrative documents, Subject records shall be appropriately filed, including the following:

- Signed informed consent forms
- Source documents used for recording data (e.g., device characteristics at implant and follow-up)
- Records of any adverse event, including supporting documentation
- Records pertaining to Subject deaths during the study
- Relevant source data
- Any other records required by the Sponsor
- Documents showing the dates and reasons for each deviation from the CIP

10. Study Management

10.1. Committees and Independent Review

10.1.1. Data Monitoring Committee

A Data Monitoring Committee (DMC, or sometimes referred to as a Data and Safety Monitoring Board or DSMB) will be established according to ISO 14155, FDA and NIH guidelines, and will consist of experienced and knowledgeable professionals who are not Investigators. The DMC will meet periodically, or as needed, to review the results of the study and to provide safety oversight and professional input to make recommendations for the continuation or termination of the study based on data analysis and study related adverse events. The members of the committee will have access to all adverse event data and any other requested study data that would be necessary in order for the group to make an assessment relative to Subject safety.

10.1.2. Adjudication Committee

As per ISO 14155, the Sponsor is responsible for the classification of adverse events and ongoing safety evaluation of the clinical investigation.

An Adjudication Committee will be established to adjudicate reported AEs.

The Adjudication Committee will consist of at least three independent physicians (i.e.: not Investigators), of whom two will form a quorum, and none are also members of the DMC. The activities will be governed by a Charter.

10.1.3. Independent Assessment of Surgical Candidacy

If the site determines that the subject is not excluded based on the MRI assessment, the site will upload the relevant images to a Core Lab for storage and preparation for review by an Independent Physician Reviewer. An appropriately trained independent physician will review the Subject's MRI to assess any current indication for back surgery according to appropriate evidence or guidelines (e.g.: Evidence Informed Management of Chronic Low Back Pain with Surgery,⁶⁸ the Guidelines of the American Pain Society,⁶⁹ or the European Guidelines for Management of Chronic Non-Specific Low Back Pain²). The activities will be governed by a Charter.

10.2. Study Principal Investigator Review

The Study Principal Investigator will review Baseline data for all subjects to confirm that they meet the eligibility criteria for the trial. This review will take place prior to the study implant procedure (Visit 2) and will be communicated to the Site Principal Investigator and study staff. The review may be performed by the Study PI or an alternate physician designated by the Study PI.

10.3. Procedures to Amend the Clinical Investigation Plan

From time to time, an Investigator or the Sponsor may propose changes to the Clinical Investigation Plan. The Sponsor shall have final authority to make such changes or not.

From time to time, the DMC may mandate or recommend changes to the Clinical Investigation Plan. From time to time, regulatory authorities may mandate or recommend changes to the Clinical Investigation Plan.

All amendments to the CIP shall be agreed upon by the Sponsor and the Investigators and be recorded with a justification for the amendments. In all cases of changes to the Clinical Investigation Plan, the local rules for approval of modifications shall be followed, including by way of example a submission to the IRB or Ethics Committee (either in full or to the Chairman), and modifications to the clinical Trial contract with the institution if applicable.

10.4. Device Accountability

Device accountability shall be in compliance with ISO 14155 and FDA regulations.

The Sponsor will control the availability of all investigational devices (including software) by shipping devices only to trained representatives or study Investigators who have IRB or Ethics Committee, and Sponsor approval. The Sponsor shall keep records to document the physical location of all investigational devices from shipment of investigational devices to the investigation sites until return or disposal. Devices are not transferable between Investigators unless prior approval is obtained from the Sponsor. Access to investigational devices shall be controlled and the investigational devices shall be used only in the clinical investigation and according to the Clinical Investigation Plan.

The site Principal Investigator or an authorized designee shall keep records documenting the receipt, use, return and disposal of the investigational devices, which shall include

1. the date of receipt,
2. identification of each investigational device (batch number/serial number or unique code),
3. the expiry date, if applicable,
4. the date or dates of use,
5. Subject identification,
6. date on which the investigational device was returned/explanted from the Subject, if applicable, and
7. the date of return of unused, expired or malfunctioning investigational devices, if applicable.

An out-of-service product is defined as any implantable products (e.g. device, lead) removed or rendered inactive. Out-of-service product includes but is not limited to devices that do not function appropriately at implant and explanted product. Whenever possible, any out-of-service product should be returned to the Sponsor for analysis. In the event of a Subject death, every effort should also be made to return product to Mainstay Medical.

10.5. Labeling

All investigational devices will have a clinical investigation label, which will be visible on the pertinent shipping cartons and storage containers. The required labels or manuals will bear the following information:

- Model and serial number of the device (the magnet does not have a serial number)
- Name of the device and the address of Mainstay Medical as the manufacturer
- Caution statement regarding investigational device

- All relevant contraindications, hazards, adverse effects, interfering substances or devices, warnings and precautions

10.6. Data Monitoring Plan

It is the responsibility of the Sponsor to ensure proper monitoring of the study per regulations. Appropriately trained Sponsor personnel or delegates appointed by the Sponsor will perform study monitoring at the investigation site in order to ensure that the study is conducted in accordance with the CIP, the signed Clinical Trial Agreement, and applicable regulatory requirements. The Sponsor must therefore be allowed access to the Subjects' clinic and hospital records when so requested as per the consent form, Privacy Authorization (US only) and Clinical Trial Agreement. Procedures required in this CIP require source document verification for this study. A separate Monitoring Plan will detail levels of source verification for this study.

Monitoring visits will be conducted periodically to assess study progress, the Investigator's adherence to the CIP and regulatory compliance. This includes but is not limited to IRB/EC approval and review of the study, maintenance of records and reports, review of the consent process and review of source documents against Subject case report forms to ensure data points are correct and that adverse events are being reported. Monitors facilitate site regulatory and study compliance by identifying findings of non-compliance and communicating those findings along with recommendations for preventative/corrective actions to site personnel. Communication with the site personnel occurs during the visit and following the visit via a written follow-up letter. Monitors may work with study personnel to determine appropriate corrective action recommendations and to identify trends within the study or at a particular center.

Frequency of monitoring visits will occur based on Subject enrollment, timing of the study visits, duration of the study, study compliance, findings from previous monitoring visits and any suspected inconsistency in data that requires investigation. All data used for a regulatory submission will be monitored against source documentation prior to the PMAA submission.

All active sites will have a closure visit. A closure visit is a visit that occurs after a site's last required follow-up visit. Closure visit activities may include source verification of the data and closure of any findings and/or study-related activities.

Storage and accountability of investigational product used for this study will be assessed and monitored throughout the study at each site.

10.7. Sponsor Responsibilities

MML US Inc. (a subsidiary of Mainstay Medical Limited, Ireland) ("Mainstay") is the Sponsor of this study, where a Sponsor is defined as an individual or organization taking the responsibility and liability for the intention or implementation of a clinical investigation.

It is the responsibility of the Sponsor to ensure proper monitoring of the study and to see that all clinical requirements are met. In addition, Sponsor representatives may participate in the conduct of the Trial to the extent described in the following section on the role of the Sponsor representatives. In this study Sponsor representatives are not blinded to the study results, particularly since Sponsor representatives may be involved in device programming. Participation in the study will be limited to Sponsor personnel who are appropriately qualified and trained such as those personnel with an engineering, technical or nursing degree or equivalent training, or significant experience within the implantable device industry. All Sponsor personnel will be trained on the appropriate clinical study regulations and guidelines for medical device trials.

It is the responsibility of the Sponsor to ensure appropriate training of all individuals involved in the clinical Trial. This includes Investigators and other health care professionals at the investigational sites, Sponsor personnel, and contractors if applicable.

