11.5. Clinical Research Organizations (CROs)

Data collection will be performed with an electronic Case Report Form (eCRF). A CRO will manage the clinical database and will be responsible for randomization. The Sponsor will determine the data monitoring staff using the Sponsor's and the CRO's personnel. Subsidiary CROs may be used in certain countries.

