This Statistical Analysis Plan (SAP) describes the statistical methods to be used during the reporting and analysis of data collected under the ReActiv8-B Clinical Investigation Plan (CIP).

2. Scope

This SAP should be read in conjunction with the CIP and case report forms (CRFs). This version of the SAP has been developed with respect to the CIP version 950057, Rev A and updated per 950057, Rev B. Any further changes to the CIP or CRFs may necessitate updates to the SAP.

3. Primary Efficacy Objective

The Primary Efficacy Endpoint is a comparison of responder rates between Treatment and Control groups, where a “responder” is a Subject with $\geq 30\%$ reduction from baseline in average low back pain VAS without any increase from baseline in pain medication and/or muscle relaxants prescribed and taken in the two weeks prior to the Primary Endpoint Assessment Visit.

Note: The primary outcome measure is intended to assess the efficacy of 120 days of stimulation. Thus the visit for assessment of the primary outcome must occur no sooner than 120 days post randomization.

4. Secondary Efficacy Objectives

There are six specified secondary efficacy objectives. The first five objectives have associated endpoints and hypotheses and will be statistically tested at the Primary Endpoint Assessment Visit. The sixth objective, consisting of multiple endpoints, will be evaluated after the Outcome Post Crossover Visit but does not have associated statistical hypotheses.

1. Comparison of change from baseline in Oswestry Disability Index (ODI) between Treatment and Control groups at the Primary Endpoint Assessment Visit
2. Comparison of change from baseline in EQ-5D between Treatment and Control groups at the Primary Endpoint Assessment Visit
3. Comparison of Percent Pain Relief between Treatment and Control groups reported by the Subject at the Primary Endpoint Assessment Visit
4. Comparison of Subject Global Impression of Change at the Primary Endpoint Assessment Visit
5. Comparison of number of Subjects with Resolution of Low Back Pain (remitters or cure, defined as a VAS score $\leq 2.5\text{cm}$) at the Primary Endpoint Assessment Visit
6. Evaluation of changes in primary and secondary efficacy metrics in the Crossover group following the Outcome Post Crossover Visit.

5. Trial Design

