8.7. Interim Analysis

A single interim analyses of the primary efficacy endpoint will occur when at least 50% of the original planned study enrollment has completed the Primary Endpoint Assessment Visit. This analysis will be limited to results from this cohort and will be used for purposes of a potential adaptive sample size increase. The interim analysis plan has the following characteristics:

- Only a single interim analysis is planned.
- The interim analysis can lead only to an increase in the study size, not a decrease in sample size or early study termination for benefit.
- If the conditional power at the time of the interim analysis is less than 30% or greater than 90%, then there will be no change in the study size. If between 30% and 90%, the study size may be increased up to a maximum of twice its originally designed size (that is, 2 x 116) to regain the original 80% power objective.
- The interim analysis will be performed by a third-party independent statistician under the direction of the Data Monitoring Committee (DMC), and detailed interim results, other than a DMC recommendation regarding the findings, will remain blinded to the sponsor and other study participants to prevent introduction of operational bias.

- On the basis of the interim analysis, the DMC may recommend one of three actions: continue the study as is, increase the sample size, or as is always an option, potentially stopping the study for reasons of safety or futility.

At the time of an interim analysis, based on the estimated conditional power, a sample size re-estimation may be performed using the method of Cui et al.^a The results will not be used to decrease the original sample size estimate or provide a basis for early study stopping for positive efficacy results. However, if it is determined that an excessive number of additional Subjects are required, a decision to recommend stopping the study early for futility may be made.

Since there is no potential for early termination benefit, no alpha adjustment to the final p-value is required other than that associated with the use of the Cui et al procedure.

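### Protocol 10.7 says Sponsor representatives are not blinded to study results, which contradicts and undermines the SAP 8.7 rule that keeps interim results from the Sponsor

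*Protocol*

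**What the plan says.** Protocol 10.7 (Sponsor Responsibilities): "In this study Sponsor representatives are not blinded to the study results, particularly since Sponsor representatives may be involved in device programming".

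SAP 8.7 (Interim Analysis) places the interim analysis with an independent statistician working under the DMC. It then says that "detailed interim results, other than a DMC recommendation regarding the findings, will remain blinded to the sponsor and other study participants", and gives the avoidance of operational bias as the reason.

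The Sponsor also holds the main levers over conduct:

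- Protocol 9.2: "Except in emergency situations, protocol deviations require prior Sponsor approval".
- Protocol 10.3, on changes to the plan: "The Sponsor shall have final authority to make such changes or not".
- Protocol 10.13.3 and 10.15: the Sponsor may end a noncompliant Investigator's participation and may suspend or terminate the trial.
- SAP 2 (Scope) sets no cut-off date for revision: "Any further changes to the CIP or CRFs may necessitate updates to the SAP".

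**The concern.** An adaptive trial with one unblinded interim look depends on the people who run it not knowing how the arms compare. SAP 8.7 claims that property for the Sponsor, and Protocol 10.7 denies it in plain words. If Sponsor staff can see outcomes by arm while Subjects are being recruited and followed, then decisions on deviations, amendments, sites, stopping and SAP changes could be influenced by the emerging result. The claim in SAP 8.7 could then be challenged from the Sponsor's own protocol when a positive primary result is submitted.

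**Working it through.** The plan gives no figure on this point, so most of the check is a comparison of texts.

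**1. Is there a real conflict?** Protocol 10.7 speaks of results and says representatives are not blinded to them. SAP 8.7 says the Sponsor stays blinded to detailed interim results. Protocol 4.13 and SAP 2 say only that the two documents are to be read together, so neither takes precedence.

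**2. Does the stated reason support the sentence?** Protocol 6.4 has Treatment devices set to a level suited to the Subject and Control devices set to the control programme. Whoever programmes the device learns the arm. Nothing in that task requires the VAS or medication outcome. The reason covers allocation only.

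**3. Can Sponsor personnel learn allocation?** Yes. Protocol 4.11 and 10.8 let them help with programming when asked. In addition, threshold measurements are Treatment-only at Visits 4 to 7 (Protocol 6.4 to 6.7 and Table 2), so the device data themselves show the arm.

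**4. Can they see outcomes?** Yes. Protocol 10.8 lets Sponsor representatives review collected data and fill in worksheets. Protocol 10.6 lets Sponsor personnel monitor, with access to clinic records and source verification. Protocol 11.5 confirms the staffing: "The Sponsor will determine the data monitoring staff using the" personnel of both the Sponsor and the CRO. Protocol 10.13.2 does not name who reviews the case report forms, so nothing here rests on it.

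**5. Are the roles separated?** Not in these documents. The list of blinded persons in Protocol 4.9 omits the Sponsor. No text keeps staff who know allocation away from outcomes, keeps either group apart from decision-makers, or forbids an outcome table by arm before lock.

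**6. Which decisions are exposed, and what limits them?**

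| Sponsor decision | Stated limit |
|---|---|
| Approve deviations (Protocol 9.2) | IRB or Ethics Committee approval where scientific soundness or Subjects' rights, safety or welfare may be affected |
| Change the plan (10.3) | Agreed with Investigators, justification recorded, local approval rules apply |
| End an Investigator's participation (10.13.3) | Repeated noncompliance |
| Suspend or stop (10.15) | Documented reasons, justified in writing |
| Update the SAP (SAP 2) | None stated |

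Deviations also bear on analysis: SAP 8.2 removes Subjects with major deviations from the Per-protocol set, and SAP 8.6 names that set for the secondary endpoints.

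**7. What does the planned adjustment cover?** Assume equal weights, since the look is planned at about 50%. The weighted statistic of the method cited in SAP 8.7 is then Z = √0.5·Z1 + √0.5·Z2. Under the null, Z2 is standard normal given Z1 whatever second-stage size is chosen, so Z has variance 0.5 + 0.5 = 1 and the two-sided error is 5%. A simulation of 2,000,000 null trials gave 0.0503. This holds whoever sees the data, but only for a data-driven choice of second-stage size with weights fixed in advance. It gives no protection to the decisions in step 6.

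**The case against.** The best defence is that 10.7 uses results loosely where it means allocation. The sentence concerns representatives in a field role and gives programming as its reason. Nothing in it grants access to DMC output, and SAP 8.7 is the more specific text. That may well be the intent, but the sentence would still need correcting, and the missing role separation would remain.

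Three stronger readings are tempting, and the documents do not support them.

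- *That 10.7 cancels the firewall.* Neither text overrides the other. The independent statistician and the restriction on DMC output remain in place.
- *That the Sponsor holds arm and outcome for every Subject.* Programming help is given on request, a CRO manages the database and randomization (11.5), Sponsor personnel not needed for data collection are kept out of that session (4.11), and they may not enter eCRF data (10.8). Protocol 4.9 also asks Subjects not to describe their sensations to Sponsor personnel. Access is possible, not shown to be complete.
- *That a particular inflated type I error follows.* Such a figure needs an assumed pattern of unplanned looks or a choice among final sizes. SAP 8.7 rules out early stopping for benefit, and SAP 6.1 rules out a decrease. The counts of 116 and 128 are one target before and after the attrition allowance, not two stopping points. Success also requires a difference favouring Treatment (SAP 8.5.1), so false positives counted in both directions would overstate false success.

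The limits in the table are also real. They govern how a decision is approved and justified. They do not prevent the person proposing it from having seen results by arm.

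**Conclusion.** The concern holds as a contradiction between the documents and as a gap in role separation. The protection that SAP 8.7 claims is not secured as written, because the Protocol says the opposite and leaves routes to both allocation and outcome open to Sponsor personnel. It should be corrected, since the trial's success rests on a single primary test.

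The size cannot be expressed as an error rate from these documents. The planned sample size increase is not compromised, provided the weights are fixed in advance. The exposure is operational bias from unplanned decisions.

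This rests on reading 10.7 as worded and on the Protocol and SAP alone. The Monitoring Plan and the DMC Charter are referred to but not included. If they already separate these roles, what remains is a wording correction. Nothing here shows that anyone looked at results by arm.

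**What to change.** Replace the sentence in Protocol 10.7 with:

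*Sponsor or CRO field staff who programme devices may know the allocation of the Subjects they programme. Apart from the independent statistician and the DMC, no Sponsor or CRO staff tabulate or have access to outcome data summarised by arm until the primary database is locked. Sponsor staff who decide on deviations, amendments, site termination, study stopping or SAP changes have no access to Subject allocation or to interim results before that lock.*

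Then:

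- Exempt the CRO randomization function, which must hold allocation. Also allow for individual emergency unblinding under Protocol 4.9, which is reported on a deviation form.
- Align Protocol 10.8 so that field staff who know allocation do not review efficacy outcome data.
- Do not extend the allocation ban to every monitor. Treatment-only device data at Visits 4 to 7 would reveal the arm during source verification. For monitors, the bar on by-arm summaries is the workable control.
- In SAP 2, state that changes after the interim data cut are made only by persons without access to by-arm data.

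The cost is wording, database access restrictions and role separation within existing Sponsor and CRO staff. The small downside is that someone who programmes devices can no longer also review efficacy data.
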